2.2 Secondary Aims

- 2.2.1 To estimate the rate of local tumor progression after SBRT.
- 2.2.2 To estimate the rate of distant disease progression after SBRT.
- 2.2.3 To measure overall survival after SBRT.
- 2.2.4 To estimate a dose-response between radiation dose and local control.
- 2.2.5 To measure longitudinal quality of life before and after SBRT.

- 2.2.6 To determine the correlation between quality of life, and disease progression after SBRT.
- 2.2.7 To determine if any dose-volume parameters predict grade ≥ 3 duodenal toxicity.
- 2.2.8 To determine if patients are able to receive additional chemotherapy after SBRT.
- 2.2.9 To identify natural anatomical surrogates that best correlate with the motion of the fiducial markers.
- 2.2.10 To determine if adaptive RT would be beneficial.

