10.0 PATIENT ASSESSMENTS

10.1 Study Parameters

Table 2

Study Procedures	Pre-Treatment	Week 1	Post-Treatment ^b
Informed Consent	X		
History and Physical	X		
Physical Exam with Vital Signs	X	X	1,3,6,9, 12 months, and every 6 months thereafter
CBC with differential, and comprehensive metabolic panel ^a	X		

CA 19-9	X		3, 6, 12, and every 6 months thereafter, or until disease progression
CT Abdomen, and Pelvis	X		3, 6, 12, and every 6 months thereafter, or until disease progression
Treatment: SBRT		D1-5	
Clinical evaluation for Toxicity	X	X	1,3,6,9, 12 months, and every 6 months thereafter
EORTC QLQ C-30/PAN26 questionnaire ^c	X		1,3,6,9, 12 months, and every 6 months thereafter

^a Electrolytes including Creatinine, Bilirubin, SGOT, and SGPT

^b Visit should occur at timepoints above +/- 28 days

^c See appendix for details on questionnaire

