12.1.2 Secondary Endpoints

12.1.2.1 Local control. The cumulative incidence of local failure will be determined for all patients treating distant progression or death as a competing

risk. Local progression will be defined as a $\geq 20\%$ increase in size on CT compared with CT prior to SBRT.

12.1.2.2 Distant metastatic progression rate. The cumulative incidence of distant metastatic failure will be determined for all patients treating death as a competing risk. In patients initially presenting with locally advanced disease, distant disease progression will be defined as the appearance of new metastatic lesions. In patients presenting with metastatic disease, distant progression will be defined as a $\geq 20\%$ increase in size on CT of the previously noted metastatic lesions.

12.1.2.3 Overall survival. Overall survival will be measured from the date of diagnosis through death of any cause. Survival will also be reported from the date of SBRT for comparisons to other trials in the literature. Finally, survival will be stratified by those with locally advanced disease, and those with metastatic disease on presentation.

12.1.2.4 Dose response. An exploratory analysis evaluating for a correlation between radiation dose response and local control will be done with a competing risk analysis, dividing patients into two groups stratified by the median dose..

12.1.2.5 Longitudinal quality of life. We will track longitudinal quality of life using the European Organization for Research and Treatment in Cancer (EORTC) quality of life core cancer questionnaire with the pancreatic cancer module (EORTC QLQ C-30/ PAN26) (see appendix). The questionnaire will be given prior to treatment, and periodically during follow-up visits after treatment has concluded. Trends will be assessed with a linear mixed effects model.

12.1.2.6 Correlation between quality of life and disease progression. Disease progression is a commonly used surrogate endpoint in clinical trial with pancreas cancer, however its relationship with quality of life has not clearly been demonstrated. Therefore, we will assess for correlation between quality of life and local or distant disease progression.

12.1.2.7 Dose-volume relationship with duodenal/gastric toxicity. We will plan to use logistic regression models to determine the relationship between grade ≥ 3 duodenal or gastric toxicity and dose to these structures. The dose to the duodenum will be extracted from our treatment planning system.

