12.2 Trial Design, Sample Size, and Study Duration

12.2.1 Trial Design: We will use a time to event continual reassessment method (TITE-CRM) trial design [11] to enroll a maximum of 30 patients onto this protocol.

The primary goal of this trial will be to determine the SBRT dose associated with a dose-limiting toxicity (DLT) in 20% of patients. DLT will be defined as grade ≥ 3 gastrointestinal toxicity (defined further below).

The TITE-CRM extends the original CRM by weighting each patient's contribution to the likelihood function described below. To determine the recommended dose for a newly enrolled patient, model parameters are estimated via the weighted likelihood. All previously enrolled patients who had either experienced toxicity or had completed the 12-month observation period without toxicity are assigned weights of 1; otherwise they are assigned weights equal to the proportion of the observation period they have completed.

The first patient in this study will enroll at dose level #2. Dose de-escalation can occur at anytime, though dose escalation will be restricted to 1 level between sequential patients. Additionally, before escalating the dose to the next level two conditions must be met: 1) the sum of the observation periods for all patients at the current dose level must be at least 12 months; and 2) at least one patient must have been under observation for at least 6 month at the current dose level. The rationale for these two conditions is mainly due to the short life expectancy of this patient population, which has a median survival of 8.25 months.

A two-parameter logistic regression model will be used to estimate the probability of toxicity at each dose level after each patient has been enrolled, which will inform the decision as to whether we should dose-escalate the patient in question. A final two-parameter logistic model will be fitted using follow-up data from 6 months after accrual of the last patient

Table 3. A priori toxicity estimation

Dose level	Probability of dose limiting toxicity
1	0.01
2	0.05
3	0.10
4	0.20
5	0.30

12.2.2 Dose Limiting Toxicity: The only toxicity observed thus far in pancreas SBRT has been related to nearby normal gastrointestinal organs, namely the duodenum and

stomach. Dose limiting toxicity in this study will be defined as any grade 3-5 gastrointestinal toxicity as measured by the Common Terminology for Adverse Events, version 4.0 (see appendix).

12.2.3 Maximum Sample Size: 30

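### Local progression is referenced only to the pre-SBRT CT, so the regrowth needed to count as a local failure rises with the initial response; where tumors shrink, failures are called late and some never.

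*Combined protocol and SAP*

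**What the plan says.** Section 12.1.2.1 counts a local failure when the primary shows at least a 20% "increase in size on CT compared with CT prior to SBRT". That is the only criterion. Neither this section nor any other adds a smallest-size or best-response reference, a new-local-lesion rule or a clinical criterion. RECIST appears only in the eligibility criteria (3.1.2 and 3.2.6). The word size is not tied to diameter, area or volume.

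The analysis in the same section reads: "The cumulative incidence of local failure will be determined for all patients treating distant progression or death as a competing" risk. Section 12.1.2.4 uses the local-control endpoint for an exploratory dose-response comparison, "dividing patients into two groups stratified by the median dose". This serves the secondary aim "To estimate a dose-response between radiation dose and local control" (2.2.4). Section 12.1.2.6 relates quality of life to local or distant progression.

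Table 2 in section 10.1 schedules abdominal and pelvic CT at "3, 6, 12, and every 6 months thereafter, or until disease progression", so there is no CT at 9 months. Section 12.2.1 describes a population "which has a median survival of 8.25 months" and plans "to enroll a maximum of 30 patients onto this protocol". Section 12.2.4 guarantees the last patient 6 months of follow-up.

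**The concern.** With a fixed pre-treatment reference, a tumor that responds must first regain everything it lost and then add 20% of its original size. Two tumors regrowing at the same rate from the same date are called at different times, and the better responder is called later.

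In many settings this would only delay the call. Here a delay can become a loss: death and distant progression compete with local failure, CTs are 6 months apart after month 6, and survival is short. A patient whose tumor is regrowing may leave the risk set without a local failure on record.

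Three secondary analyses use the definition: the local progression rate (aim 2.2.1), the dose-response comparison (aim 2.2.4) and the quality-of-life correlation (aim 2.2.6). In the second, the distortion could run along the variable being compared, because dose may influence shrinkage.

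**Working it through.** The documents give no expected rate, precision or power for local control (Tables 4 and 5 concern the MTD), so there is no stated figure to reproduce.

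**Step 1: regrowth required.** Set the pre-SBRT size to 1 and the smallest size to 1 - s. The rule is met at 1.2, so regrowth from the smallest size must reach 1.2/(1 - s) - 1.

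| Shrinkage s | 0% | 5% | 10% | 20% | 30% | 40% | 50% |
|---|---|---|---|---|---|---|---|
| Regrowth needed | 20% | 26% | 33% | 50% | 71% | 100% | 140% |

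With the smallest size as reference, the figure is 20% throughout.

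**Step 2: added delay.** If size doubles every T months during regrowth (assumed), the extra time is T × log2(1/(1 - s)). For T = 3, 6 and 9 months:
- s = 30%: 1.5, 3.1 and 4.6 months
- s = 10%: 0.5, 0.9 and 1.4 months

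The call then waits for the next CT. With exponential survival and the stated 8.25-month median, 1 - 0.5^(6/8.25) = 40% of patients alive at 6 months die before 12.

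**Step 3: 12-month incidence of local failure, by simulation.** From the documents: CTs at 3, 6 and 12 months, and median survival 8.25 months (taken as exponential). Assumed: linear shrinkage over 3 months (mean s, SD 5 points), exponential time to regrowth onset, exponential regrowth, and distant progression either absent or with a 9-month median. A call requires the patient to be alive and free of distant progression at the CT. Entries are protocol rule / smallest-size rule, then the gap in points.

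| Distant progression | Doubling time (months) | Median onset (months) | s = 10% | s = 30% |
|---|---|---|---|---|
| none | 6 | 6 | 34.2 / 37.1 (2.9) | 27.8 / 36.6 (8.8) |
| none | 6 | 12 | 20.9 / 23.0 (2.1) | 16.2 / 22.6 (6.4) |
| none | 12 | 6 | 24.7 / 27.9 (3.2) | 13.8 / 26.1 (12.3) |
| none | 12 | 12 | 14.5 / 17.0 (2.5) | 7.4 / 15.8 (8.4) |
| 9 months | 6 | 6 | 20.4 / 22.4 (2.0) | 15.7 / 21.7 (6.0) |
| 9 months | 6 | 12 | 12.0 / 13.4 (1.4) | 8.9 / 12.9 (4.0) |
| 9 months | 12 | 6 | 12.4 / 13.6 (1.2) | 7.0 / 11.8 (4.8) |
| 9 months | 12 | 12 | 7.2 / 8.2 (1.0) | 3.7 / 7.1 (3.4) |

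Fixing shrinkage at exactly 30% raises the largest gap to 12.9 points. The range is thus about 1 to 3 points at 10% shrinkage and 3 to 13 at 30%.

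**Step 4: dose comparison.** Regrowth onset (median 6 months) and doubling time are the same in both groups. Mean shrinkage is 10% at lower dose and 30% at higher dose (assumed). Rejection is for a pooled two-proportion z test at two-sided 5% with 15 v 15 patients.

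| Distant progression, doubling time | Protocol rule, low v high dose | Gap (points) | Gap, smallest-size rule (points) | Rejection, protocol / smallest-size |
|---|---|---|---|---|
| none, 6 months | 34.4% v 27.7% | 6.7 | 0.7 | 7.4% / 5.0% |
| none, 12 months | 24.6% v 13.6% | 10.9 | 1.9 | 11.4% / 5.5% |
| 9 months, 6 months | 20.4% v 15.6% | 4.8 | 1.0 | 6.3% / 5.3% |
| 9 months, 12 months | 12.5% v 7.0% | 5.5 | 1.9 | 4.0% / 3.9% |

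Gaps are from unrounded values.

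**Step 5: noise cost of the alternative.** Take a tumor that shrinks 30% and never regrows, with independent measurement error at each CT (assumed). False calls by 12 months under the smallest-size rule are 0.6% at 5% error, 6.1% at 8% and 10.9% at 10%. Under the protocol rule they are about 0%.

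**Step 6: the undefined measure.** A 20% rise in volume is 1.2^(1/3) - 1 = 6% in diameter. A 20% rise in diameter is 1.2^3 - 1 = 73% in volume.

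**The case against.** Several objections have force.

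- **Shrinkage is not documented.** At 10% the loss is only 1 to 3 points. This stands: a reader might infer that aim 2.2.1 is understated outright, but the documents support that only to the extent that tumors shrink.
- **The trial is imprecise anyway.** With 30 patients and a 25% failure proportion, the 95% half-width is 1.96 × √(0.25 × 0.75/30), about 15 points, which exceeds the largest loss found. True, but the error runs in one direction and costs little to remove.
- **A false dose-response is not established.** It needs deeper shrinkage at higher dose, which the documents neither show nor exclude. Keeping a tumor below its pre-treatment size for longer could itself be read as a dose effect. The analysis is labelled exploratory, and spurious significance rises only modestly. All of this stands; what remains is a possible tilt in the estimates.
- **Phase II.** A reader might infer that the follow-on trial would be misled. The documents do not support this: section 1.4 carries the MTD into phase II, and sections 12.1.1 and 12.2 derive the MTD from gastrointestinal toxicity alone. No rule uses local control to choose a dose.
- **Survival and competing events.** Section 1.2 gives a median of 10 to 12 months, against 8.25 in section 12.2.1. Repeating step 3 with 11 months made the gaps larger, not smaller. Distant progression removes some cases under either rule; the settings that include it still show a loss.
- **Noise.** At 8 to 10% measurement error, the false calls in step 5 are comparable in size with the failures recovered. This stands, and is the reason to report both results.

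**Conclusion.** The point holds in a limited form. That required regrowth rises with response is arithmetic and follows from the definition alone. Its size rests on assumed shrinkage, regrowth and distant-progression rates. Of the failures a smallest-size rule would count by 12 months at 30% shrinkage, the protocol rule leaves out roughly a quarter to a half (24% to 53% in step 3). At 10% shrinkage the effect is small. The direction was the same in every setting with shrinkage.

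For dose-response, the conclusion is conditional: if shrinkage deepens with dose, the estimates could favour higher dose by about 5 to 11 points in the settings tried, with no difference in regrowth. The endpoint is secondary. Dose assignment, the MTD and the choice of phase II dose do not depend on it. The change is worth making because it is cheap and makes the called failure rate largely independent of the initial response.

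**What to change.** In 12.1.2.1, define local progression as an increase of at least 20% in a stated measure of the primary tumor, for example its longest diameter, over the smallest measurement since and including the pre-SBRT CT. If the tumor never shrinks, the reference stays the pre-SBRT CT. State the measure in the same sentence, because step 6 shows that it sets the threshold. Use the definition in 12.1.2.1, 12.1.2.4 and 12.1.2.6, and report the result referenced to the pre-SBRT CT as a supportive analysis.

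The cost is a sentence or two of text, with no added scans or readers. The smallest-size reference is more exposed to measurement noise, and the reported failure rate will be less favourable. Showing both results lets a reader judge how much of the difference could be noise.

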3.1 Inclusion Criteria

- 3.1.1 Diagnosis: Histologically-proven invasive adenocarcinoma of the pancreas.
- 3.1.2 Disease Status: Medically unresectable (stage I-II), or locally advanced (stage III). Patients with distant metastases (stage IV) must have stable disease or improved disease (partial response, or complete response) per Response Evaluation Criteria In Solid Tumors (RECIST) criteria as determined on serial imaging following a course of chemotherapy.
- 3.1.3 Tumor Location: Primary tumor may be located anywhere in the pancreas.
- 3.1.4 Treatment eligibility: The patient must be able to have fiducial markers implanted into the pancreatic tumor, and receive radiation regimen as specified in the protocol.
- 3.1.5 Performance Level: Karnofsky Performance Status ≥ 60 (see Appendix II)
- 3.1.6 Adequate Renal Function Defined As:
 - Serum creatinine $\leq 1.5 \times$ upper limit of normal
- 3.1.7 Age: Patients must be 18 years of age or older.
- 3.1.8 Informed Consent: All subjects must sign a written informed consent.

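### Section 12.1.2.2 does not count new metastases as distant progression in patients presenting with metastatic disease, yet pools them with patients in whom new metastases are the event

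*Combined protocol and SAP*

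**What the plan says.** Secondary aim 2.2.2 is "To estimate the rate of distant disease progression after SBRT". Section 12.1.2.2 sets the estimator: "The cumulative incidence of distant metastatic failure will be determined for all patients", with death as the competing risk. It then gives two event definitions.

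- Patients initially presenting with locally advanced disease: "distant disease progression will be defined as the appearance of new metastatic lesions".
- Patients presenting with metastatic disease: at least a 20% "increase in size on CT of the previously noted metastatic lesions".

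Section 3.1.2 admits stage IV patients, who "must have stable disease or improved disease (partial response, or complete response") after chemotherapy, so complete responders can enrol.

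Distant progression is used again in two places. In 12.1.2.1 the local-failure incidence "will be determined for all patients treating distant progression or death as a competing" risk. In 12.1.2.6, "we will assess for correlation between quality of life and local or distant disease progression".

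**The concern.** The second definition is confined to lesions already known. Read literally, a patient who presented with metastases, whose old lesions are stable and who develops a new one, is scored as free of distant progression. The same CT finding in a patient who presented with locally advanced disease is an event. A complete responder may have no visible lesion from which to calculate a percentage increase. If new sites do not count either, that patient may have no reachable distant event.

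The two definitions are then combined in one curve, so the answer to aim 2.2.2 depends partly on the case mix. The definition also decides when the distant competing event occurs in 12.1.2.1 and how patients are classified in 12.1.2.6. It would also enter the dose-response analysis in 12.1.2.4 if that uses the same competing events, which 12.1.2.4 does not state.

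**Working it through.** **Does another section repair the definition?** No. RECIST is cited only for eligibility (3.1.2 and 3.2.6), not for this endpoint. Reporting by locally advanced versus metastatic disease is planned only for survival (12.1.2.3).

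**Direction.** Adding an event type to the metastatic group can only raise its cumulative incidence or leave it unchanged. The locally advanced rule already counts new lesions. The pooled estimate is therefore at or below the one that counts new lesions in everyone. The two are equal if no patient under the growth-only rule has a new lesion without, or before, qualifying growth.

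**Size.** The plan states no expected rate or precision for this endpoint, so there is no figure to reproduce. What follows is an illustration.

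Input from the documents: median survival 8.25 months (12.2.1), taken as exponential, so d = ln2/8.25 = 0.0840 per month.

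Assumed inputs:
- distant hazard h = ln2/6 = 0.1155 or ln2/12 = 0.0578 per month, equal across stages;
- share p of metastatic-group progressions that are by new lesions only: 25%, 50% or 75%;
- growth hazard of old lesions after a new one appears: unchanged (m = 1) or tripled (m = 3);
- metastatic share of the cohort: 20% to 40%.

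New lesions counted: CIF(12) = h/(h+d) × [1 − exp(−12(h+d))].
- 6-month distant median: 0.1155/0.1995 × (1 − 0.0912) = 0.526.
- 12-month distant median: 0.0578/0.1418 × (1 − 0.1824) = 0.333.

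As the plan is written, let g = (1−p)h, n = ph, a = h+d and b = mg+d. Then

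CIF(12) = (g/a)(1 − e^(−12a)) + [mgn/(a−b)] × [(1 − e^(−12b))/b − (1 − e^(−12a))/a].

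With m = 1 this reduces to the first formula with h replaced by (1−p)h. Pooled shortfall = metastatic share × difference.

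| Distant median | p | m | New lesions counted | As written | Pooled shortfall, 20% to 40% metastatic |
|---|---|---|---|---|---|
| 6 mo | 25% | 1 | 52.6% | 44.2% | 1.7 to 3.4 points |
| 6 mo | 25% | 3 | 52.6% | 48.3% | 0.9 to 1.7 |
| 6 mo | 50% | 1 | 52.6% | 33.3% | 3.9 to 7.7 |
| 6 mo | 50% | 3 | 52.6% | 41.0% | 2.3 to 4.7 |
| 6 mo | 75% | 1 | 52.6% | 19.0% | 6.7 to 13.5 |
| 6 mo | 75% | 3 | 52.6% | 27.4% | 5.0 to 10.1 |
| 12 mo | 25% | 1 | 33.3% | 26.6% | 1.3 to 2.7 |
| 12 mo | 25% | 3 | 33.3% | 28.8% | 0.9 to 1.8 |
| 12 mo | 50% | 1 | 33.3% | 19.0% | 2.9 to 5.7 |
| 12 mo | 50% | 3 | 33.3% | 22.4% | 2.2 to 4.4 |
| 12 mo | 75% | 1 | 33.3% | 10.2% | 4.6 to 9.3 |
| 12 mo | 75% | 3 | 33.3% | 13.3% | 4.0 to 8.0 |

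Upper corner written out: 0.25h = 0.0289; 0.0289/0.1129 × (1 − e^(−1.355)) = 0.190; 0.40 × (0.526 − 0.190) = 13.5 points to rounding.

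**Comparison with sampling error at n = 30.** The binomial standard error is sqrt(0.526 × 0.474/30) = 9.1 points, or sqrt(0.333 × 0.667/30) = 8.6 points. At p = 50% the shortfall (2.2 to 7.7 points) is smaller than this. At p = 75% it can be larger.

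**The case against.** The strongest reply concerns scope. Section 12.1.2.2 classifies patients by how they presented and does not say whether that means at diagnosis or at enrolment. A patient diagnosed with locally advanced disease who later became metastatic and responded to chemotherapy is eligible as stage IV. If presentation means diagnosis, that patient falls under the new-lesion rule. This stands. A reader might infer that new metastases are ignored in every stage IV patient, but the text does not establish that: stage IV at enrolment is only an upper bound on the group affected.

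Second, a reader might infer that the pooled rate is materially biased low. The documents support only at or below. Some new-lesion events are delayed rather than lost, because old lesions may grow later. The model also detects events continuously, whereas Table 2 schedules CT at 3, 6 and 12 months. Scoring events only in patients alive at those scans changes the p = 50% range from 2.2-7.7 to 1.8-6.6 points. Against that, Table 2 continues CT only until disease progression. If a new lesion is treated as progression and CT stops, later growth would not be captured and the delayed event would be lost.

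The opposite inference, that the shift must be small beside sampling error, is not supported either. It holds at p = 50% but not across the range.

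Third, one might add that stage I-II patients, listed in 3.1.2 apart from stage III, have no rule. The same two-way split is used for survival in 12.1.2.3, so it most plausibly works as non-metastatic versus metastatic. That is missing detail, not an error.

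Finally, this is one of ten secondary aims in a dose-finding trial of at most 30 patients. That limits the importance of the point but does not correct the definition.

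**Conclusion.** The definition in 12.1.2.2 is wrong as written. It leaves out new metastases in patients presenting with metastatic disease and pools them with patients in whom new metastases are the event. That conclusion and its direction follow from the text and need no assumptions.

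The size is unknown. Under the illustrative assumptions the 12-month pooled shortfall is roughly 1 to 13.5 points. It could be zero, and it is smaller if presentation means diagnosis and few patients were metastatic at that time. It is a systematic error that a larger sample would not remove.

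The effect is confined to secondary endpoints. Nothing in the documents links this definition to dose-limiting toxicity, so the MTD, the TITE-CRM design and the sample size are unaffected.

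**What to change.** In 12.1.2.2, replace the two definitions with one for all patients: distant progression is the appearance of a new metastatic lesion (including reappearance of one that had resolved), or an increase of at least 20% in the size of known metastases compared with the CT before SBRT. Section 12.1.2.1 already uses that reference scan. Apply the definition wherever distant progression is used: 12.1.2.1, 12.1.2.6, and 12.1.2.4 if it shares those competing events.

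Also report the incidence separately for patients without and with metastatic disease at enrolment. Even under one definition, growth of known metastases is possible only in the second group. Fixing the grouping at enrolment removes the doubt about presentation.

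The cost is a sentence of text and one extra split in reporting, with no new scans or visits. The reported distant rate stays the same or rises. The first-event local failure rate falls slightly because more competing events are counted. For illustration, take p = 50%, m = 1 and a local hazard of −ln(0.84)/12 = 0.0145 per month, from the 84% one-year figure that section 1.4 cites for a different, single-fraction regimen. Local failure in the metastatic group then falls from 7.9% to 6.3% (6-month distant median) or from 8.9% to 7.9% (12-month median). In the whole cohort that is 0.2 to 0.6 points at a 20-40% metastatic share. The change should be made before outcomes are scored.

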3.2 Exclusion Criteria

- 3.2.1 Pregnancy or Breast-Feeding: Pregnant or breast-feeding women will not be entered on this study due to risks of fetal and teratogenic adverse events. (Note: Serum Pregnancy tests must be obtained in women of child bearing potential). Sexually active females may not participate unless they have agreed to use an effective contraceptive method (such as abstinence, diaphragm, condom, or intrauterine device) to prevent pregnancy for the duration of the study.

- 3.2.2 Life expectancy < 6 months
- 3.2.3 The patient cannot have had prior radiation therapy to the thorax or upper abdomen.
- 3.2.4 Incarcerated individuals
- 3.2.5 Subjects unable to give informed consent
- 3.2.6 Subjects with uncontrolled distantly metastatic disease per RECIST criteria (progressive disease) on imaging following chemotherapy

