6.1.0.2 Imaging

All subjects will undergo a 3-dimensional (3D) CT scan with intravenous contrast, and slice thickness ≤ 2.5 mm. This 3D scan should preferably be done during an expiratory breath hold phase. Following the 3D CT, a four-dimensional (4D) CT scan with respiratory gating will be done to account for tumor motion. CT scans should include T4/T5 to L5/S1.

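### Progression is a 20% increase in an undefined size with no absolute minimum, so in patients presenting with metastases small lesions can be called progressed on measurement variation

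*Combined protocol and SAP*

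**What the plan says.** Section 12.1.2.1 defines local progression as a ≥20% "increase in size on CT compared with CT prior to SBRT". Section 12.1.2.2 splits distant progression by disease status. For patients presenting with locally advanced disease, "distant disease progression will be defined as the appearance of new metastatic lesions". For patients presenting with metastatic disease, it is a ≥20% "increase in size on CT of the previously noted metastatic lesions".

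The two outcomes are linked in the analysis. Section 12.1.2.2 says "The cumulative incidence of distant metastatic failure will be determined for all patients treating death as a competing" risk, and section 12.1.2.1 says "The cumulative incidence of local failure will be determined for all patients treating distant progression or death as a competing" risk.

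RECIST appears only at entry. Under 3.1.2, stage IV patients "must have stable disease or improved disease (partial response, or complete response) per Response Evaluation Criteria In Solid Tumors (RECIST) criteria". Under 3.2.6 the excluded group is "Subjects with uncontrolled distantly metastatic disease per RECIST criteria (progressive disease) on imaging following chemotherapy". Section 12.1.2 does not refer to it.

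Table 2 schedules CT at 3, 6 and 12 months and every 6 months after that, or until disease progression.

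**The concern.** A purely relative threshold becomes very small in millimetres when the lesion is small. Stage IV patients enter only with stable or responding disease after chemotherapy, so small residual metastases are plausible. For a single 10 mm lesion measured by diameter, 2 mm is enough. Each scheduled CT is a further chance to cross the line by measurement variation alone.

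The text also leaves open what is measured (diameter, area or volume), whether the rule applies to each lesion or to their total, whether a second scan must confirm the call and, for metastases, which scan is the baseline. Two readers of the same images could reach different answers.

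The secondary estimates are at stake:
- A false distant call is an event in 12.1.2.2.
- It is a competing event in 12.1.2.1, so it takes the patient out of the local-failure risk set and carries into the dose-response comparison in 12.1.2.4.
- It is a misclassified progression in the quality-of-life correlation in 12.1.2.6.
- Under Table 2 it can end the imaging that would have corrected it.

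With at most 30 patients, one misclassified patient is 1/30 = 3.3 percentage points of a crude proportion.

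**Working it through.** The plan states no error rate, event count or power for progression, so there is no figure to reproduce.

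**Inputs from the documents.** The 20% rule with no minimum (12.1.2.1, 12.1.2.2), and three CTs in the first year (Table 2).

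**Assumptions.** The documents give neither lesion size nor measurement error. I take single lesions of 10, 20 and 30 mm and independent normal error with SD 1.0–1.5 mm per measurement, and show a wider SD range below.

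**Step 1: what 20% means.** As a diameter it is 20%. As an area it is 1.2^(1/2) − 1 = 9.5% in diameter. As a volume it is 1.2^(1/3) − 1 = 6.3%. On a 10 mm lesion these are 2.0, 1.0 and 0.6 mm. If size is a sum of diameters, 2 mm is 10% of a 20 mm total and 6.7% of a 30 mm total, so it does not count.

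**Step 2: one scan, unchanged lesion of diameter d.** The rule is met when follow-up − 1.2 × baseline ≥ 0. That quantity has mean −0.2d and standard deviation SD × √(1 + 1.2²) = 1.562 × SD. The probability is therefore 1 − Φ(0.2d / (1.562 × SD)).
- 10 mm: 2/1.562 = 1.28 gives 10.0% (SD 1.0); 2/2.343 = 0.854 gives 19.6% (SD 1.5).
- 20 mm: 4/1.562 = 2.56 gives 0.5%; 4/2.343 = 1.71 gives 4.4%.
- 30 mm: 6/1.562 = 3.84 gives about 0%; 6/2.343 = 2.56 gives 0.5%.

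**Step 3: any of three scans.** The scans share one baseline, so the three chances are not independent. These figures come from simulation (400,000 draws per cell). The last two columns add an absolute minimum of 5 mm.

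| Lesion | 20% rule, SD 1.0 | 20% rule, SD 1.5 | With 5 mm, SD 1.0 | With 5 mm, SD 1.5 |
|---|---|---|---|---|
| 10 mm | 20.6% | 36.3% | 0.06% | 2.5% |
| 20 mm | 1.4% | 10.0% | 0.06% | 2.5% |
| 30 mm | about 0% | 1.3% | about 0% | 1.3% |

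Over a wider SD range, the three-scan figure at 10 mm is 1.4% for SD 0.5 mm and 45.4% for SD 2.0 mm; in the latter case the 5 mm minimum lowers it to 9.3%. At 50 mm it is at most 0.2% throughout.

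**Step 4: where the minimum acts.** 20% of 25 mm is 5 mm. If size means diameter, a 5 mm minimum changes nothing from 25 mm upward.

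**The case against.** The 10 mm case is close to the worst case, and lesion size drives the result: at SD 1.0 mm the three-scan figure falls from 20.6% at 10 mm to 1.4% at 20 mm. The case also needs size to mean one lesion's diameter, while the text speaks of lesions in the plural. Three scans require a 12-month CT, yet section 12.2.1 gives a median survival of 8.25 months, so many patients will have fewer looks. The rule covers only patients presenting with metastases, whose number is not stated. The endpoint is a descriptive secondary one. All of this stands, and it limits the size of the problem. It does not supply the missing definition.

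Four stronger readings are tempting, but the documents do not support them.

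- *Distant progression is overstated.* A reader might infer this from the false-call rates. The same sentence, however, does not list new lesions as progression in patients presenting with metastases, which pushes the estimate down. The net direction is unknown.
- *The rule calls changes that CT cannot resolve.* The "slice thickness ≤ 2.5 mm" limit in 6.1.0.2 is for the simulation CT. No slice thickness is given for follow-up CT, and slice thickness does not set the precision of a diameter measured within an axial image.
- *Local failure is inflated because size may be read as volume.* Section 6.1.1.3 contours the pancreatic tumor on the planning CT only, and nothing asks for re-contouring at follow-up. On a diameter reading, a 30 mm primary has a three-scan risk of at most 1.3% for SD up to 1.5 mm.
- *RECIST already governs.* The documents use it for entry only, so no minimum can be assumed from it.

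**Conclusion.** The concern holds in limited form. Both definitions lack an absolute minimum and a definition of size, and the metastatic rule also lacks a baseline scan. Small residual metastases can therefore be called progressed on measurement variation. The risk is material near 10 mm, modest at 20 mm and negligible from about 30 mm, under an assumed SD of 1.0–1.5 mm and a single-lesion diameter reading. The documents do not show that such miscalls will be common, because they give neither lesion sizes nor measurement error.

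The effect is confined to secondary estimates: distant progression in patients presenting with metastases and, through competing events, local failure, the dose-response comparison and the quality-of-life correlation. The MTD rests on gastrointestinal toxicity and is unaffected. This is worth correcting because the correction is cheap, not because it threatens the trial's primary aim.

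**What to change.** In 12.1.2.1, define local progression as a ≥20% increase in longest diameter from the pre-SBRT CT **and** an absolute increase of at least 5 mm. In 12.1.2.2, for patients presenting with metastases, apply the same two conditions to the sum of longest diameters of the known metastases, with the pre-SBRT CT as baseline, **and** count any new lesion as distant progression. The last clause is needed: a rule limited to baseline lesions would fix the present omission in place, and it would not work for complete responders, who are eligible under 3.1.2 and have no lesion to measure.

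The 5 mm figure is a proposal and does not come from the documents. The alternative is one sentence stating that a named RECIST version with an absolute minimum, as part of the criteria already used for eligibility, governs both progression endpoints.

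Either route costs a sentence or two per definition and uses the same scans. The downside is that true growth of very small lesions is called slightly later.
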